5.1. Determination of Sample Size

Approximately 500 patients will be randomized at a 4:1 ratio in the blinded Induction Period to receive 250 mg mirikizumab or placebo SC at Weeks 0, 4, 8, and 12. Stratified block randomization will be performed with the following stratification factors: previous exposure to biologic therapy (yes/no), body weight (<100 kg or ≥100 kg), and geographic region (North America or Other).

There are multiple primary endpoints in this study: static Physician’s Global Assessment (sPGA) (0,1) and PASI 90 at Week 16. The assumed sPGA (0,1) responses are 70% for the mirikizumab arm and 5% for the placebo arm. The assumed PASI 90 responses are 70% for the mirikizumab arm and 3% for the placebo arm. These assumptions are based upon the results of

the mirikizumab Phase 2 Study AMAF (Reich et al. 2017) and review of historical clinical studies in psoriasis (Langley et al. 2014; Gordon et al. 2016; Blauvelt et al. 2017; Papp et al. 2017; Reich et al. 2017).

With a total sample size of 500 patients, randomizing 400 patients to the mirikizumab arm and 100 patients to the placebo arm, this study has power of >95% for testing superiority of mirikizumab to placebo based on a 2-sided chi-square test with alpha of 5% on sPGA(0,1). It also provides a power of >95% for testing superiority of mirikizumab to placebo on PASI 90 based on a 2-sided chi-square test with alpha of 5%.

In order to account for multiple testing for the comparisons of 2 mirikizumab groups against the placebo group in the Maintenance Period, a 2-sided chi-square test at the 0.025 level is assumed. Assuming 70% of the mirikizumab patients are re-randomized in the Maintenance Period at Week 16 (Visit 7) at a 1:1:1 ratio to 250 mg mirikizumab Q8W, 125 mg mirikizumab Q8W or placebo, approximately 93 patients will be included in each treatment group. Stratified block randomization will be performed with the stratification factor of body weight at baseline (<100 kg or \geq 100 kg). This sample size will provide >95% power to test the difference in the proportion of patients maintaining PASI 90 from Week 16 (Visit 7) after re-randomization at the start of the Maintenance Dosing Period to Week 52 (Visit 16) between each mirikizumab dosing interval and placebo, assuming the proportions of patients maintaining PASI 90 are 80% for 250 mg mirikizumab Q8W, 70% for 125 mg mirikizumab Q8W, and 10% for placebo.

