In addition, when specified as a sensitivity analysis, pseudo-likelihood-based mixed-effects model of repeated measures (Categorical MMRM) estimating the percentage of patients achieving response across postbaseline visits may be used. When MMRM is used, the model includes treatment, baseline value (continuous), visit, the interaction of the baseline value-by-visit, the interaction of treatment-by-visit, and the induction/maintenance covariates mentioned in Section 6.2 as fixed factors. The binomial distribution and the logit link function will be used. The residual pseudo-likelihood with a subject-specific expansion (RSPL) will be used, which is equivalent to restricted maximum likelihood (REML). An unstructured covariance matrix will be used to model the within-patient variance-covariance errors. If the unstructured covariance matrix results in a lack of convergence, the heterogeneous Toeplitz covariance structure, followed by the heterogeneous autoregressive covariance structure will be used. The Kenward-Roger approximation will be used to estimate the denominator degrees of freedom. The Newton-Raphson with ridging optimization technique will be used to aid with convergence. The probability of response, the corresponding 2-sided 95% CI, and the p-value for the treatment comparisons at postbaseline visits will be reported.

Treatment comparisons of continuous efficacy and health outcome variables with multiple postbaseline measurements will be made using mixed-effects model for repeated measures (MMRM). When MMRM is used, the model includes treatment, baseline value, visit, the interaction of the baseline value-by-visit, the interaction of treatment-by-visit, and the induction/maintenance covariates mentioned in Section 6.2 as fixed factors. The covariance structure to model the within-patient errors will be unstructured. If the unstructured covariance matrix results in a lack of convergence, the heterogeneous Toeplitz covariance structure, followed by the heterogeneous autoregressive covariance structure will be used. The restricted maximum likelihood (REML) will be used. The Kenward-Roger method will be used to estimate the denominator degrees of freedom. Type III tests for the least squares (LS) means will be used for the statistical comparison; the 95% confidence interval will also be reported.

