Treatment comparisons of continuous efficacy and health outcome variables with a single postbaseline time point will be made using analysis of covariance (ANCOVA) with the following in the model: treatment group, baseline value, and Induction Period/Maintenance Period covariates mentioned in Section 6.2. Type III tests for LSMeans will be used for statistical comparison between treatment groups. The LSMean difference, standard error, p-value, and 95% CI, unless otherwise specified, will also be reported. Analysis of covariance may also be used in addition to the MMRM approach, by repeating analysis for each time point.

The Kaplan-Meier (KM) product limit method will be used to estimate the survival for several time to event analyses. The hazard ratio and log-rank test stratified by covariates mentioned in Section 6.2 will be reported. Time for all analysis will be described in units of weeks.

For variables that are not collected at each postbaseline visit, data may exist at visits where the variable was not scheduled to be collected. In these situations, data from the early discontinuation visit that do not correspond to the planned collection schedule will be excluded from the MMRM analysis (Andersen and Millen 2013). For by-visit summaries/displays, such as boxplots, the weeks when data was not scheduled to be collected may not be displayed. However, unscheduled assessments within any defined study period will still be used in the shift analyses, and for imputing values for the change from baseline to modified baseline observation carried forward (mBOCF) endpoint analyses.

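### The induction MMRM and ANCOVA pool one error variance across arms under 4:1 allocation, so their intervals are mis-calibrated if the arms differ in spread

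*SAP*

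**What the plan says.** SAP 6.1.4 compares continuous efficacy and health outcome variables with an MMRM or an ANCOVA.

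- **MMRM.** "The covariance structure to model the within-patient errors will be unstructured". If this fails to converge, the fallbacks are heterogeneous Toeplitz and then heterogeneous autoregressive; in both, the heterogeneity is over visits. Estimation is by REML with Kenward-Roger degrees of freedom. Protocol 10.3.1 words the covariance in the same way.
- **ANCOVA.** The model has treatment, baseline value and the stratification covariates, and "Type III tests for LSMeans will be used for statistical comparison between treatment groups".

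Neither document mentions a covariance that differs by arm or a robust standard error for these models.

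On allocation, SAP 5.1 says "Approximately 500 patients will be randomized at a 4:1 ratio in the blinded Induction Period", and it bases power on "randomizing 400 patients to the mirikizumab arm and 100 patients to the placebo arm". On response, "The assumed PASI 90 responses are 70% for the mirikizumab arm and 3% for the placebo arm". No SD is given for any continuous endpoint.

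SAP Table AMAK.6.6 applies MMRM, ANCOVA or both to changes in PASI, BSA, PSS, PSSI, PPASI, NAPSI, DLQI, SF-36, WPAI-PSO and others. The primary endpoints and all multiplicity-controlled secondary endpoints are binary and analysed by CMH with NRI (Protocol 10.3.3.1; SAP 6.10.1 and 6.10.3, Table AMAK.6.6).

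**The concern.** With equal arms, pooling unequal variances leaves the standard error of a difference in means correct in large samples. At 4:1 it does not. The pooled variance mostly reflects the 400 mirikizumab patients, while the sampling error of the difference comes mostly from the 100 placebo patients. If those 100 are more variable, the reported interval is too short; if less variable, too long.

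Nothing else in the specification corrects this. Kenward-Roger is a small-sample adjustment within the assumed covariance model. The fallback structures change the pattern over visits, not its equality across arms.

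There is a reason to expect unequal spread for PASI-type scores. Percent improvement cannot exceed 100, and the plan expects 70% of mirikizumab patients to lie between 90 and 100. Placebo patients have no such compression, and worsening counts as a negative value (SAP Table AMAK.6.5). At stake is the calibration of the induction 95% intervals and p-values for continuous endpoints.

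**Working it through.** **1. The plan's own figures.** Two-sided tests at 5% with 400 versus 100 patients, for 70% versus 3% and 70% versus 5%, have power above 0.999, which agrees with the stated >95%. Re-randomized group size: 400 × 0.70 / 3 = 93.3, which agrees with about 93. These confirm the inputs but contain no information on continuous-scale SDs.

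**2. Effect of pooling.** Let r = placebo SD / mirikizumab SD, with mirikizumab SD = 1.

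- True variance of the difference: 1/400 + r²/100.
- Pooled-model variance: (0.8 + 0.2r²) × (1/400 + 1/100) = (0.8 + 0.2r²) × 0.0125.
- Coverage of a nominal 95% interval: 2Φ(1.96 × model SE / true SE) − 1.

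Example, r = 2: model 1.6 × 0.0125 = 0.0200; true 0.0025 + 0.0400 = 0.0425; SE ratio √(0.0200/0.0425) = 0.686; coverage 82.1%.

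| r | model SE / true SE | coverage |
|---|---|---|
| 0.79 | 1.15 | 97.6% |
| 1 | 1.00 | 95.0% |
| 1.2 | 0.90 | 92.1% |
| 1.5 | 0.79 | 87.9% |
| 2 | 0.69 | 82.1% |
| 3 | 0.59 | 75.5% |

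At 1:1 allocation the same formula gives 95.0% for every r.

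**3. Check by simulation.** ANCOVA with 400/100 patients, a baseline covariate and eight strata, 4,000 runs per ratio:

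| r | pooled variance | HC3 |
|---|---|---|
| 1 | 95.1% | 95.2% |
| 1.5 | 88.3% | 95.2% |
| 2 | 82.7% | 95.3% |
| 3 | 75.7% | 94.9% |

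A further run at r = 0.8 also gave about 95% with HC3, so the remedy works in either direction.

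**4. What 70% and 3% say about r.** One threshold per arm does not determine an SD. Shapes that all meet the two rates for PASI percent improvement, each an assumption, give:

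- Common latent normal with SD 15 to 50 points, capped at 100: r = 1.58 to 2.08, coverage 87% to 81%.
- Lognormal residual PASI ratio with common log-SD 0.4 to 1.0: r = 2.6 to 11, coverage 77% to 68%.
- Mirikizumab non-responders uniform on 50 to 90, placebo non-responders uniform on −20 to 60: r = 1.96, coverage 82.5%.
- Mirikizumab non-responders uniform on 0 to 90, placebo non-responders uniform on −20 to 90: r = 1.22, coverage 91.9%.
- Mirikizumab non-responders uniform on 0 to 90, placebo non-responders uniform on −10 to 50: r = 0.79, coverage 97.6%.

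The last case by hand, with responders uniform on 90 to 100:

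- Mirikizumab variance = 0.7 × 8.33 + 0.3 × 675 + 0.21 × 50² = 733, SD 27.1.
- Placebo variance = 0.03 × 8.33 + 0.97 × 300 + 0.0291 × 75² = 455, SD 21.3.
- Ratio 21.3 / 27.1 = 0.79.

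**5. Maintenance (1:1:1).** With the two mirikizumab arms equally variable, SE ratio = √[2(2 + r²) / (3(1 + r²))]. At r = 2 this is √0.80 = 0.894, coverage 92.0%. At r = 3 it is √0.733 = 0.856, coverage 90.7%.

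**The case against.** The strongest reply is that the documents contain no SD, so the direction of the error is unproven. Step 4 shows that the 70% and 3% rates fit a placebo arm that is less variable than mirikizumab. This stands. A reader might infer from the rates that placebo spread must be much larger and that the induction intervals are therefore too narrow. The documents support only that they may be. The shapes with r at or below 1 do need mirikizumab non-responders spread evenly down to no improvement, whereas SAP 5 allows for partial or slow responders among them. That makes r > 1 plausible, not established.

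A second reply concerns scope. A reader might extend the point to every continuous endpoint, but the rates concern PASI 90 and sPGA (0,1). They say nothing about the spread of SF-36, WPAI-PSO or NAPSI. For PSSI and PPASI the argument is by analogy only. PASI change and BSA change, where it is most direct, are analyses added in the SAP and not protocol-listed endpoints. This stands too.

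Third, no decision under error control depends on these models. A reader might suspect inflated Type I error, but the testing graph in SAP 6.5 covers only the primary and major secondary endpoints, all analysed by CMH with NRI.

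Fourth, for PASI the effect would swamp the error. Assume SDs of 42.5 and 16 (r = 2.66) and a difference of 76 points. The true SE is √(16²/400 + 42.5²/100) = 4.32, giving z = 17.6. The pooled SE is √[(0.8 × 16² + 0.2 × 42.5²) × 0.0125] = 2.66, giving z = 28.6. The conclusion is the same, but the 95% half-width should be 8.5 points and would be reported as 5.2. The objection stands for the significance decision, not for the interval, which SAP 6.1.4 says will be reported.

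**Conclusion.** The point holds conditionally. As written, and by the usual software default, both induction models use one error covariance for the two arms; the SAP does not say so outright, but specifies nothing else. Under 400:100 allocation the intervals are correctly calibrated only if the arms have equal spread. Coverage falls to about 92%, 88%, 82% and 75.5% at SD ratios of 1.2, 1.5, 2 and 3, and rises to 97.6% at 0.79.

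A ratio above 1 is plausible for PASI-type scores because of the ceiling. Its size rests on assumed distributions and cannot be computed from the documents, and they support no such claim for SF-36, WPAI-PSO or NAPSI. Primary and major secondary results and the controlled Type I error are unaffected. Maintenance at 1:1:1 is only mildly exposed: about 91% to 92% at ratios of 3 and 2, and SAP 6.3.2 keeps only pre-relapse visits in that MMRM, which limits placebo spread.

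Confidence is high for the mechanism and moderate for the magnitude. The change is worth making because it is cheap and gives valid intervals whichever arm is more variable.

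**What to change.** In SAP 6.1.4, for the induction continuous endpoints:

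- **MMRM:** fit a separate unstructured matrix per treatment group (REPEATED with GROUP=treatment), keeping Kenward-Roger. If this does not converge, use empirical (sandwich) standard errors and name the degrees-of-freedom method that goes with them.
- **ANCOVA:** use HC3 standard errors or a group-specific residual variance.

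Applying the same to maintenance is optional.

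The cost is about one sentence and one model option. With five post-baseline induction visits (Weeks 2, 4, 8, 12, 16), an unstructured matrix has 5 × 6 / 2 = 15 parameters, so two arms need 30. Convergence is most at risk in the placebo subsets with scalp, nail or palmoplantar involvement, which the sandwich fallback is there to cover. Intervals will usually be wider. Because Protocol 10.3.1 carries the same covariance wording, the change and its justification would also have to be described in the clinical study report.

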6.2. Adjustments for Covariates

Unless otherwise specified, the statistical analysis models for the Induction Period efficacy will include adjustment for the covariates: previous exposure to biologic therapy (yes/no), body weight (<100 kg or ≥100 kg), and geographic region (North America or Other). In all models, the adjustment for covariates will be performed by coding each of 8 possible combinations of the covariates as a separate strata, and the strata will be actual the variables adjusted for. Similarly, unless otherwise specified, the statistical analysis models for the Maintenance Period efficacy will adjust for the covariate body weight (<100 kg or ≥100 kg). These covariates correspond to the stratification factors to be used during randomization. When MMRM or ANCOVA is used, additional covariates, such as baseline, will be used, as described in Section 6.1.4.

6.3. Handling of Dropouts or Missing Data

Intercurrent events (ICH E9R1) are events which occur after the treatment initiation and make it impossible to measure a variable or influence how it should be interpreted. Examples of such events include treatment discontinuation due to death or adverse events (AEs), rescue treatment, and loss to follow-up. The missing data methods described below handle intercurrent events in different ways.

6.3.1. *Non-Responder Imputation (NRI)*

The NRI method can be justified based on the composite strategy (ICH E9R1) for handling intercurrent events. In this strategy patients are defined as responders only if they meet the clinical requirements for response at the predefined time AND they remain on the assigned study treatment. Failing either criteria by definition makes them non-responders.

Analysis of binary efficacy and health outcome variables will be assessed using an NRI method. Patients will be considered as non-responder for the NRI analysis if they do not meet the clinical response criteria or have missing clinical response data at the analysis time point. Randomized patients with no postbaseline observations will also be defined as non-responders for the NRI analysis.

For the Maintenance Period, patient who relapse (see definition in [Table AMAK.6.5](#)) after re-randomization during the maintenance period will be considered to have entered the relapse period and will be non-responders for all subsequent visits of maintenance efficacy analysis.

For the Relapse Period, the response rates will be summarized by the weeks after relapse based on the number of patients with planned scheduled visit during the Relapse Period. Patients who complete the Week 52 treatment visit will, thereafter, not be counted in the numerator when calculating the response rate.

6.3.2. Mixed-effects Model for Repeated Measures (MMRM)

The MMRM method can be justified based on the hypothetical strategy (ICH E9R1) for handling intercurrent events. In this strategy, the scientific question of interest is to assess the effect of study treatment in a hypothetical trial where all patients have complete data and continue to take study treatment without dropping out of the study or receiving rescue therapy.

MMRM will be used where specified for longitudinal continuous measurements. It assumes missing data can bias results, but the bias can be attenuated by modeling random effects using the within-patient error correlation structure. These correlations between the repeated measurements provide the platform used to account for the bias from patient dropout. MMRM model details are provided in [Section 6.1.4](#).

If patients enter the Relapse Period, only the visits prior to entering the Relapse Period will be included in the MMRM model for the Maintenance Period efficacy analysis.

6.3.3. Modified Baseline Observation Carried Forward (mBOCF)

An mBOCF analysis will be performed on specified continuous efficacy endpoints. For patients discontinuing investigational product due to an AE, the baseline observation for the endpoint will be carried forward to the corresponding visit for all missing observations after the patient discontinued study treatment. For patients discontinuing investigational product for any other reason, the last nonmissing postbaseline observation before discontinuation will be carried forward to the corresponding visit for all missing observations after the patient discontinued. For all patients with sporadically missing observations prior to discontinuation, the last non-missing observation before the sporadically missing observation will be carried forward to the corresponding visit. Randomized patients without at least 1 postbaseline observation will not be included for evaluation with the exception of patients discontinuing study treatment due to an AE.

The mBOCF can be justified based on the composite strategy (ICH E9R1) for handling intercurrent events. It handles the intercurrent event of discontinuing study drug due to an

adverse event by defining the patient as not receiving any benefit from study drug after the event. That is, the patient is defined as reverting back to baseline regardless of any continuing efficacy benefits they may still have received after the event. For other intercurrent events (e.g., rescue treatment and discontinuation due to reasons other than an AE) the while on treatment strategy is applied. That is, the endpoint is defined as the last observed value at or before the visit of interest while the patient was still on study drug.

6.3.4. As Observed

Summary based on observed data at each postbaseline visit will be provided for some endpoints. Descriptive statistics will be reported without inferential comparisons. Only data from completers at the visit are relevant, and therefore the analysis does not need to deal with missing data. This estimand is based on the subset of patients who would complete treatment through visit if assigned to it. Therefore, this estimand is conditional and targets the effect of treatment conditional on completion of treatment through the time point of interest. Because the estimand is defined for a subpopulation conditional on an intercurrent (post-randomization) event, it is not causal. The strategy used in this estimand is the one behind the so-called “observed cases” or “completers” analysis ubiquitous in the literature but is not one of the recommended strategies in the ICH E9(R1).

6.3.5. Tipping Point Analysis

Tipping point analysis will be conducted as sensitivity analysis for primary endpoints including PASI 90 and sPGA (0,1) at Week 16.

Within each analysis, the most extreme case will be considered, in which all missing data for patients randomized to mirikizumab will be imputed using the worst possible outcomes and all missing data for patients randomized to placebo will be imputed with the best possible outcomes:

- Missing responses in the mirikizumab group will be imputed with a range of response probabilities, including probabilities of 0, 0.2, 0.4, 0.6, 0.8, and 1.0.
- For missing responses in the placebo group, a range of response probabilities, probabilities of 0, 0.2, 0.4, 0.6, 0.8, and 1.0, will be used to impute the missing values. Multiple imputed data sets will be generated for each response probability.

Treatment differences between mirikizumab and placebo will be analyzed for each imputed data set using Cochran-Mantel-Haenszel test (Section 6.1.4). Results across the imputed data sets will be aggregated using SAS[®] Proc MIANALYZE in order to compute a p-value or 95% CI for the treatment comparisons for the given response probability. If the probability values do not allow for any variation between the multiple imputed datasets (for example, all missing responses in the placebo and mirikizumab groups are imputed as responders and nonresponders, respectively), then the p-value from the single imputed dataset will be used.

6.4. Multicenter Studies

[figure not shown]
This study will be conducted by multiple investigators at multiple sites internationally. Typically, a logistic regression with treatment, center, and treatment-by-center may be used to

assess the consistence of treatment effect in center. However, due to a large number of sites in the study, this logistic regression model will not likely converge. Instead, the subgroup analysis on the country, and the region will be evaluated. The countries will be categorized into geographic regions: Asia (Japan, Korea, Taiwan), North America (United States, Puerto Rico), Central America/South America (Mexico), and Europe (Germany, Poland, Russia). Subgroup analysis details are provided in Section 6.14.1.

If the treatment-by-country or treatment-by-region interaction is significant at a 2-sided alpha level of 0.1, the nature of this interaction will be inspected as to whether it is quantitative (i.e., the treatment effect is consistent in direction across all countries or regions, but not in size of treatment effect) or qualitative (the treatment is beneficial in some, but not all countries or regions). If the treatment-by-country or treatment-by-region interaction effect is found to be quantitative, results from the primary model will be presented. If the treatment-by-country or treatment-by-region interaction effect is found to be qualitative, further inspection will be used to identify in which countries or regions mirikizumab is found to be more beneficial.

